Complete the Questionnaires assigned to you by selecting “My Surveys”

HUDSONALPHA
INSTITUTE FOR BIOTECHNOLOGY

Complete the Questionnaires assigned to you by clicking on a “Current Questionnaire” being sure to **reference the Study ID Number**

[figure not shown]
- Research nurse will complete assigned surveys in Genome Gateway.
 - These surveys are focused on phenotypes, previous genetic testing, prenatal testing (if known) and the enrollment process. (see screenshot steps below)
 - This information will be accessible to the analysis team at HudsonAlpha.

Select the patient from the list. Click Assign on Return of Results Baseline Questionnaire

[figure not shown]
Select due date from the calendar. Click Assign.
Reminders will be preset at defined times

- The due date should be up to ROR (roughly 2 ½ months for baseline). All subsequent surveys will be set 1-month from the day you assign the survey.
- The due date reminders will be automatically preselected for you (2-day before, 7-days before, and 14-days before)
- Research nurse will ship samples to the Clinical Services Laboratory at HudsonAlpha and submit them for sequencing via online portal.
- The research nurse will upload the W9 (needed for payment) and the informed consent form to GG.
 - Screenshots highlighting how to upload documents are below.

Uploading Documents to Genome Gateway

Navigate to “Files” from the homepage

To upload a file, select patient, then click “+”

Write message to send with file below

Choose File no file selected

1. Click "Choose File" - a finder window will open
 2. Select file (any file type) from correct location on computer
 3. Click "Choose"
 4. Click "Upload" to send it to the patient

**A message can be included with the file in the text box

- Forms/survey measures completed at enrollment
 - Informed Consent Form (ICF)- (paper form uploaded to Genome Gateway; hard copy kept in study binder)
 - W9 form (paper form uploaded to GG; hard copy kept in study binder until clinical trial team informs the coordinator to destroy- 7 years)
 - Participant Enrollment Survey
 - Sociodemographic in GG
 - Genetic Counseling Outcome Scale (GCOS)
 - Genetic Knowledge Assessment (GKA)
 - Visual Analog Scale (VAS)- Child's Health
 - Parental Perceptions of Uncertainties in Genomic Sequencing (PUGS)
 - Health Literacy
 - Subjective Numeracy Scale (SNS)
 - 12-item Short Form Survey (SF-12)
 - Medical Outcomes Survey (MOS)
 - Research Nurse/Coordinator Surveys (phenotype, other genetic testing, enrollment notes, etc.)

If a parent/caretaker participant doesn't respond to the baseline measures, the clinical trial team will contact the study coordinator, to remind the participant to complete surveys via GG and/or over the phone, after a biweekly data pull is completed to generate a list of non-completers. All data collected pre-ROR, will still be valid as baseline data.

(2) Return of Results (ROR) Visit

- After samples are sequenced, analyzed, and variants of interest have been Sanger validated (by HudsonAlpha, PerkinElmer, EGL, etc.), the HudsonAlpha analysis team will contact the clinical team and hold a variant review meeting (VRC) to discuss any findings.
- After VRC, the enrolled families will be scheduled for a return of results (ROR) appointment by the site research nurse/coordinator (preferably in-person) where a GC/healthcare provider will return the finding(s)
 - The ROR can be completed over the phone if necessary, as a last resort. Reasons for offering a phone ROR include families who are unwilling to return to clinic because of distance or psychosocial distress. Caution should be made to not let the type of result dictate the ROR setting (i.e. do not preferentially offer negative results phone disclosures and positive results in-person consultations).
 - If a phone ROR is to be completed, the same provider should do the disclosure who would have been expected to do an in-person meeting. The phone experience should be made to feel as similar to the in-person experience as possible (length, content, staff, flow).
 - **It is important that the parent/caregiver who completes the enrollment surveys continue to be the person attending and completing the ROR visit and surveys (In-clinic survey and At-home survey).**
- The research nurse will place the clinical Sanger report along with the family-friendly genetic counseling letter in the child's medical record so that clinicians will have access to the finding(s).
- The (GCOS/FACToR) ROR questionnaire is administered by the research nurse immediately following the ROR visit. After completion of the ROR visit, the 1-month post ROR, and 4-month post ROR post-enrollment can be programmed for automatic administration.
 - If completed over the phone, the answers need to be recorded on paper, and uploaded to Genome Gateway
- Forms/survey measures completed at ROR visit
 - Sociodemographic
 - Genetic Counseling Outcome Scale (GCOS)
 - **This survey needs to be administered by the research nurse/coordinator after ROR. This is the primary outcome and needs to be completed directly after ROR.**
 - The Feelings About genomic Testing Results (FACToR)
 - **This survey needs to be administered by the research nurse/coordinator after ROR. This needs to be completed directly after ROR because it is an important covariate.**
 - Patient Assessment of Communication (Adapted from PACE) (Mazor et. al., 2016)
 - Visual Analog Scale (VAS)- Child's Health
 - Parental Perceptions of Uncertainties in Genomic Sequencing (PUGS)
 - Parental Personal Utility Scale (PrU)
 - 12-item Short Form Survey (SF-12)
 - Medical Outcomes Survey (MOS)
 - Understanding (Novel Measure)
- The research nurse/coordinator in partnership with HudsonAlpha will determine who the most appropriate clinical provider at each site is to receive the harmonized "provider survey." This provider should be the physician likely to make a clinical decision based on the WGS results at the time of ROR. If the neonate is inpatient this physician will likely be a neonatologist providing medical care for the neonate, if already discharged it could be pediatrician or another specialist depending on the neonate's symptoms. The site coordinator will determine the status of the proband (inpatient/outpatient) at the time of ROR (consulting with the family about this issue if already discharged) and will send the provider's name and contact information to [name], PhD ([contact]) within a week of

ROR appointment. Information can be sent via the Genome Gateway messaging tool. Information to be sent includes:

- Study ID
- Result type (positive/inconclusive/no finding)
- ROR date
- Clinical provider's name
- Clinical provider's contact information (email (required), phone, address)

(3) 1-month post-ROR Visit

- Forms/survey measures completed at 1-month post-ROR visit
 - Sociodemographic (if status has changed)
 - The Feelings About Genomic Testing Results (FACToR)
 - Patient Assessment of Communication (Adapted from PACE)
 - Visual Analog Scale (VAS)-Child's Health
 - 12-item Short Form Survey (SF-12)
 - Medical Outcomes Survey (MOS)
 - Understanding (Novel Measure)
 - Information Seeking

(4) 4-month post-ROR Visit

- Forms/survey measures completed at 4-month post-ROR visit
 - Sociodemographic (if status has changed)
 - The Feelings About Genomic Testing Results (FACToR)
 - Patient Assessment of Communication (Adapted from PACE)
 - Visual Analog Scale (VAS)- Child's Health
 - Parental Personal Utility Scale (PrU)
 - 12-item Short Form Survey (SF-12)
 - Medical Outcomes Survey (MOS)
 - Understanding (Novel Measure)
 - Information Seeking

(5) 4-month plus 2 weeks post-ROR Visit

- Forms/survey measures to be completed at 4-month plus 2 weeks post-ROR visit
 - Family Communication
 - Medical Actions and non-Med/Patient-Initiated Actions Attributable to Genomic Testing

3.f.3 Follow-Up of Participants during the Study

Participants will be actively followed through all study visits until completion of the study. This includes, but is not limited to:

- Genome Gateway can provide email and text reminders (if participant provided a cell phone number and consented to text reminders) to users for the purpose of notifications of due dates, new messages, new file uploads, new learning assignments, and new questionnaires.
- Research Nurses/coordinators will confirm contact information and remind the participants that they will be paid for follow-up surveys
- A generic mailing will be sent to participants to keep them engaged and informed of their participation ** pending IRB approval**

[figure not shown]
Upon onboarding of Genome Gateway, by default, all participants will receive text and email notifications from GG when any new assignment, questionnaire, files, or message is sent. The participants will have the option to decline email/text notifications during the onboarding process. They may also decline email/text notifications during the course of the trial, if the alerts become burdensome. When a provider or administrator assigns learning articles and questionnaires, a due date for those items must be set (the deadline for questionnaires is 1 month). If a due date is set for the completion of those, a set of reminders can be added which will cause an automatic email/text notification to be sent at a designated number of days before the due date. For example, it is possible to set a due date of January 12 with reminders to be sent 2, 7, and 14 days prior to the due date. This is done at the time of assignment.

3.g Safety Reporting

3.g.1 Errors in Reporting of Results

Errors will be tracked within GG utilizing a participant-specific questionnaire that is assigned to the GC completing the review. This questionnaire will ask about the length of the recording, the name of the clinician doing the disclosure, and whether any errors were noted as well as the contents of the error. The questionnaire will ask separately about each error type (safety error, major error, minor error). See Figure 2 for a breakdown of error types.

Figure 2. Types of Genetic Test Reporting Errors

Minor Errors

In the case of a minor error, these errors will be tracked internally but no intervention will be made.

Definition: Errors in the non-critical details that have little expected impact on participant understanding, decision-making and management.

Examples:

- Saying the participant “has the gene” instead of saying the participant “has a gene mutation”
- Saying the gene is on the incorrect chromosome
- Terminology misuse - heterozygous versus homozygous

Major Errors

In the case of a major error, the disclosing healthcare provider will receive a message from the reviewing GC clarifying the error and recommending he/she follow-up with the participant to convey corrected/additional information. The clinician is expected to correct the misconception both with the patient and any documentation they did clinically at their site. If the clinician asks for assistance or does not feel comfortable addressing the error, the genetic counselor will be responsive to those requests. If a participant reaches out to HA with questions, [name] will address concerns, but the disclosing healthcare provider is expected to be the one to have direct patient contact and a patient relationship.

Definition: Errors in the critical content that have a significant expected impact on participant understanding, decision-making, and/or management.

Examples:

- Wrong recurrence risk (i.e. stating recurrence risk is 25% when it is actually <1%)
- Confusion regarding etiology (*de novo*, parental carrier status)
- False reassurance (i.e. counseling that WGS will provide a concrete answer as to participant’s life expectancy)
 - Negative results and the misconception that it rules out genetic etiology (explicit statements)
- Misunderstanding of pathogenicity/penetrance
 - Likelihood of actual development of features/severity
- Incorrect understanding of a VUS (saying it is highly unlikely to be the cause/is nothing to worry about; or saying it is definitely the cause)

High-risk Safety Errors

In the case of a high-risk safety error, this will be brought to the attention of the clinical trial leadership team and the Data Safety Monitoring Board (DSMB) for recommendations on how to manage the situation.

Definition: Errors that have a high risk of immediate and detrimental impact on participant safety; should be reported to DSMB.

Examples:

- Recommendation of invasive testing or procedure based on a misinterpreted test result
- Giving back wrong result; counseling the wrong family
- Failure to report a high impact incidental finding

3.h Data and Safety Monitoring Board (DSMB) Activities

We will convene a DSMB for additional monitoring of study procedures. The safety of the study participants is the highest priority for this project. The ability to make appropriate, sound scientific decisions regarding the outcome of each participant, as early as possible, is the top priority. The DSMB will be comprised of three scientists/clinicians who are independent of the study. All safety monitoring body member(s) will complete and sign the Conflict of Interest (COI) Statement. [name] (Clinical Trial/Scientist) will provide and track the COI statements prior to providing DSMB members study materials and then track this on an annual basis. See appendix 8 for additional information.

3.h.1 DSMB Responsibilities

- Review the outcome instruments, informed consent documents and plans for data safety and monitoring
- Evaluate the progress of the clinical trial, including periodic assessments of data quality and timeliness, recruitment, accrual and retention, participant risk versus benefit, and other factors that can affect study outcome
- Consider factors external to the study when relevant information becomes available, such as scientific or therapeutic developments that may have an impact on the safety of the participants or the ethics of the trial
- Review study performance, make recommendations and assist in the resolution of problems reported by the Principal Investigator(s) (Clinical Trial PIs)
- Protect the safety of the study participants and monitor the rate and scope of errors reported in the experimental arm of the clinical trial.
- Report on the safety and progress of the trial
- Make recommendations to the PIs concerning continuation, termination or other modifications of the trial based on the observed beneficial or adverse effects of the intervention under study
- The PIs will report findings of the DSMB to NGHRI in accordance with reporting guidelines
- Ensure the confidentiality of the study data and the results of monitoring
- Assist in commenting on any problems with study conduct, enrollment, sample size, and/or data collection.

The DSMB will discharge itself from its duties when the last participant completes the clinical trial.

3.h.2 DSMB Board Process

At the initial meeting the DSMB will discuss the protocol, suggest modifications, and establish guidelines to study monitoring by the Board. The DSMB Chairperson, in consultation with the Principal Investigator and the study team, will prepare the agenda to address the review of provider education materials, modifications to the study protocol and informed consent document, initiation of the trial, reporting of return of results errors, and statistical analysis plan. Meetings of the DSMB will be held annually or more frequently at the discretion of the DSMB, if necessary. The study investigators or their designees will attend the meetings. An emergency meeting of the DSMB may be called at any time by the Chairperson or by the PIs should safety questions or other unanticipated problems arise. The meetings are closed to the public because discussions may address confidential participant data. The meetings are attended by the Principal Investigators and members of their staff. Meetings may be convened as conference calls, as well as in-person.

3.h.3 DSMB Meeting Format

DSMB meetings will consist of open and closed sessions. Discussion held in all sessions is confidential. The PI and key members of the study team attend the open sessions. Discussion will focus on the conduct and progress of the study, including participant accrual, protocol compliance, and problems encountered.

Each meeting must include a recommendation to continue or to terminate the study and whether the DSMB has any concerns about participant safety made by a formal DSMB majority or unanimous vote. Should the DSMB decide to issue a termination recommendation, the full vote of the DSMB is required. In the event of a split vote, majority vote will rule and a minority report will be appended. The DSMB Chair provides the tiebreaking vote in the event of a 50-50 split vote. A recommendation to terminate the study may be made by the DSMB at any time by majority vote. The Chair should provide such a recommendation to the PIs immediately by telephone and email.

3.h.4 Meeting Materials

A DSMB interim report template will be prepared by the study staff, typically by the study statistician, and will be reviewed by the DSMB members at the first meeting. The format and the content of the reports for, and the plans for, interim analyses will be finalized and approved at the initial DSMB meeting, although changes throughout the trial may be requested by the Board. The reports will list and summarize safety data and describe the status of the study. All meeting materials will be sent to PIs who will forward the materials to the DSMB between 7 to 14 days prior to the meeting. The reports will be numbered and provided in sealed envelopes and can be returned within an express mailing package or by secure email, as the DSMB prefers. In select cases, PIs may approve direct mailing of the reports from the study to the DSMB.

3.h.5 DSMB Reports

Reports generally include administrative reports by site that describe participants screened, enrolled, completed, and discontinued, as well as baseline characteristics of the study population, and interim error statistics from HudsonAlpha obtained through review of the ROR sessions (i.e. errors tracking). Other general information on study status may also be presented. The DSMB may direct additions and other modifications to the reports on a one-time or continuing basis. The reports may also contain data on study outcomes, including safety data, and perhaps efficacy data.

A formal report containing the recommendations for continuation of, or modification to the study will be prepared by the DSMB Chairperson, PIs, or designee. The draft report will be sent to the DSMB members for review and approval. It is the responsibility of the PIs to distribute the DSMB recommendation to all co-investigators and to ensure that copies are submitted to the IRBs. As previously stated, the formal DSMB report must include a recommendation to continue or to terminate the study. This recommendation should be made by formal majority vote. A termination recommendation may be made by the DSMB at any time by majority vote. In the event of a split vote in favor of continuation, a minority report will be contained within the regular DSMB report. See Data Safety Monitoring Plan appendix 9 for additional information.

3.h.6 DSMB Confidentiality

All materials, discussions and proceedings of the DSMB are completely confidential. Members and other participants in DSMB meetings are expected to maintain confidentiality.

3.i Study Compliance

Investigators will conduct the study in an efficient and diligent manner and in conformity with this protocol; generally accepted standards of GCP; and all applicable federal, state, and local laws, rules and regulations relating to the conduct of the clinical study. The clinical trial PI also will allow audits, IRB/Independent Ethics Committee review and regulatory

agency inspection (if required) of trial-related documents and procedures and provide for direct access to all study-related source data and documents. The investigators will prepare and maintain complete and accurate study documentation in compliance with GCP standards and applicable federal, state, and local laws, rules and regulations. Study documentation will be promptly and fully disclosed by the clinical trial PI upon request for inspection, copying, review, and audit at reasonable times by any regulatory agencies. The investigators will promptly take any reasonable steps that are requested by designated representatives as a result of an audit to cure deficiencies in the study documentation and GG surveys. Persons debarred from conducting or working on clinical studies by any court or regulatory agency will NOT be allowed to conduct or work on this study.

3.j Data Collection and Outcome Instruments

All data for this study will be collected by study staff in accordance with 21 CFR Part 11 rules and will meet all regulatory requirements. All data entry will use the Genome Gateway platform, with which our team has extensive experience. All outcome instruments will be completed electronically in the Genome Gateway platform by the participants or research nurse/study coordinator(s). Beyond the informed consent, participants will complete no paper surveys, unless there is a technical issue with the Genome Gateway platform, or a family cannot complete the survey measures online (paper copies will be used and scanned into Genome Gateway). All Genome Gateway forms filled out by participants or study personnel will be considered source documents and must be maintained in a study binder.

3.j.1 Source Documentation

All Genome Gateway forms filled out by participants or study personnel will be considered source documents and kept electronically. All electronic forms and logs in Genome Gateway platform are encrypted and password protected and hard copies can be printed if required. A detailed listing of all current study forms is below in Table 3.

Table 3. Study Forms

Form	Visit Administered	Instructions	Location
Informed Consent	Enrollment Visit	Participant/s reads consent. Study staff obtaining consent should sign, date, and time stamp	Paper, uploaded to Genome Gateway
Screening/Decliner Survey	Enrollment Visit	Completed by research nurse or study coordinator	Electronic Copy
Enrollment Survey	Enrollment Visit	Completed by parent or caregiver after study enrollment	Genome Gateway
Return of Results (ROR) Survey (In-clinic and At-home surveys)	GCOS and FACToR at ROR Visit; Additional measures after visit	Complete primary outcome measure (GCOS) and FACToR measure immediately after ROR, additional measures can be completed at participant's convenience	Genome Gateway
1-month post-ROR Survey	Complete 1-month post ROR	Complete survey online using GG	Genome Gateway
4-month post-ROR Survey	Complete 4-months post ROR	Complete survey online using GG	Genome Gateway
4-month plus 2 weeks post-ROR Survey	Complete 4-months plus 2 weeks post-ROR	Complete survey online using GG	Genome Gateway

User roles (researchers, providers, patients/participants and administrators) with secure log-in will be defined. The following information will be tracked: current user, database accessed, date, and time and the application will be stopped automatically after 15 minutes of user inactivity requiring a fresh log-in. All data will be collected via the questionnaires in Genome Gateway. The clinical trial study coordinator, clinical trial project manager and statistician will review all data collected weekly. This will help ensure all electronic forms are being completed correctly, are intact, and have been entered into system correctly.

3.j.2 General Instructions for Completing Forms

All data recorded in Genome Gateway will be maintained according to the International Council for Harmonization of Technical Requirements for Pharmaceuticals for Human Use (ICH) Good Clinical Practice (GCP) guidelines. Instructions for completing the questionnaires to ensure quality and consistency in data collection are below.

3.j.3 Retention of Study Documentation

Investigators will adhere to rigorous requirements and will retain copies of all paper (e.g. informed consent), electronic forms, and all other study documents for a period of no less than 7 years. Each site will maintain all documents, and at the close of the study UAB will retain all site documents.

3.j.4 Administrative Forms

Table 4. Administrative Forms

Form	Description	Location
Study Roster	Complete study personnel roster and signature of all members of the study team. It is the responsibility of the Principal Investigators and/or Clinical Project Manager to: designate individuals approved to make form entries and changes, and note the date when any study team member is removed from the team for any reason.	Study Binder; Table 1, section 3.b
Schedule of Visits and Evaluations	Listing of all schedule study visits and evaluations	Study Binder; Table 2, section 3.f.1
Training Log	Record of trained study personnel	Study Binder Appendix 10
Screening Log	Log of individuals screened and enrolled	Study Binder Appendix 11
Project Team Communication Log	Record of official study calls/emails between study staff	Study Binder Appendix 12

3.k Data Management

HudsonAlpha has extensive experience in data management, currently managing several studies. HudsonAlpha has developed the Genome Gateway platform that serves as a shared platform to seamlessly support data management

needs across the spectrum of this project. Genome Gateway is hosted on and data is stored on a secure, HIPAA cloud-based platform offered through Datica, Inc. Data from SouthSeq participants used by researchers and genome analysts is coded and de-identified prior to being made available to those individuals. De-identified data is stored on a secure File Transfer Protocol (FTP) server hosted by HudsonAlpha and can be tracked via a unique study ID number generated for each participant. Genome Gateway is the center of data management for SouthSeq across all sites involved in the study.

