***HudsonAlpha Genetic Counselor contacts by site:**

Alabama: [name]

Mississippi: [name]

Louisiana: [name]

Statistical Analysis Plan

Statistical Analysis: Descriptive statistics were calculated by randomized group. Specifically, for continuous demographic variables, sample means and standard deviations were calculated. For categorical demographic variables, counts and sample proportions were calculated. To test for differences between the randomized groups regarding demographics, two-sample tests were conducted for continuous variables and Chi-square analyses categorical outcomes. Sample means and standard deviations were calculated by randomization group for the primary outcome (GCOS) and secondary outcomes (PUGS, PRU). For all the outcomes, sample means and standard deviations were calculated by genetic testing results (none, variant of unknown significant, pathogenic) within each randomized group. Margin of noninferiority was set per outcome. To test non-inferiority, a one-tailed two-sample test comparing the difference of means, calculated as mean score outcome score of mother's randomized to receive genetic results from genetic counselors minus the mean score outcome score of mother's randomized to receive genetic results from non-genetic providers, to the non-inferiority margin was conducted. The normality assumption was examined using normal-probability plots and histograms. The same testing strategy was used for stratified analyses to determine if non-inferiority could be declared by genetic result types. All tests utilized a Type I error rate of 0.025 and were conducted in SAS 9.4.

Primary outcome

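### DSMB materials that may include efficacy data go through the principal investigators, and the available text does not say that by-arm or closed-session reports bypass them

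*Combined protocol and SAP*

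**What the plan says.** Section 3.h.4 (Meeting Materials) sets the default route: "All meeting materials will be sent to PIs who will forward the materials to the DSMB". The exception is also in the PIs' hands: "In select cases, PIs may approve direct mailing of the reports from the study to the DSMB". The same section adds a safeguard: "The reports will be numbered and provided in sealed envelopes".

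Section 3.h.5 (DSMB Reports) lists the usual content: participant flow by site, baseline characteristics, and error statistics from review of the result-return sessions. It then allows more: "The reports may also contain data on study outcomes, including safety data, and perhaps efficacy data". The formal report carrying the recommendation "will be prepared by the DSMB Chairperson, PIs, or designee"; DSMB members review and approve the draft, and the recommendation is by majority vote.

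On attendance, 3.h.2 (DSMB Board Process) says: "The meetings are attended by the Principal Investigators and members of their staff". Section 3.h.3 (DSMB Meeting Format) says: "DSMB meetings will consist of open and closed sessions", and places the PI and key study staff in the open ones.

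Appendix 9 (DSMB Plan and Charter) repeats all of this and adds no further restriction.

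**The concern.** A DSMB can look at results by arm during a trial because those results stay with people who are not running it. Here the default runs the other way. Everything bound for the board goes first to the PIs, and the route that avoids them needs their consent.

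What this barrier protects is any decision still open while data accumulate. Section 3.h.4 leaves the interim-analysis plans to the first DSMB meeting and lets the board ask for changes later. The protocol's description of the non-inferiority trial (3.e and 3.e.4) gives no numerical margin. The margins appear only in the SAP, which is written in the past tense alongside the results ("Margin of noninferiority was set per outcome"). The missing margin is a separate matter. It is mentioned only to show the kind of choice that investigators should not be able to make with comparative data in view.

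**Working it through.** No arithmetic applies. The check is whether the provisions, read together, keep by-arm interim results away from the PIs.

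1. **Route.** Section 3.h.4 and Appendix 9 both cover all meeting materials. No class of report is exempt by rule, and direct mailing depends on PI approval.

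2. **Content.** The usual content in 3.h.5 is administrative, plus error statistics. Outcome and efficacy data are allowed but not promised, and no sentence says that they are shown by arm. Section 3.h.1 asks the board to advise on continuation or termination from the intervention's observed benefits and harms. In a randomised comparison that is hard to do without by-arm data, but this is an inference.

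3. **Error statistics.** Section 3.e.2 tracks disclosure errors in the experimental arm only, so these figures are not comparative. Section 3.g.1 also requires high-risk errors to reach trial leadership. Passing them to the PIs is proper.

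4. **Sealed envelopes.** The sentence does not say who seals them, whether this is done before the PIs receive them, or that the PIs may not open them. If they are sealed by the preparing statistician, the PIs are only couriers. If they are sealed at the PIs' office, nothing is protected. The text fits both readings.

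5. **Attendance.** Section 3.h.2 has PIs and staff at the meetings without limit. Section 3.h.3 names open sessions for them but does not state that they are excluded from closed ones. Appendix 9 carries the same two statements.

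6. **Drafting.** PIs are among those who may prepare the formal report. The members' approval and vote limit what drafting can do.

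7. **Comparison within the protocol.** Section 3.e.1 keeps the file that tracks randomization status away from the rest of the study team. The DSMB section has no matching rule for results by arm.

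For a PI to see comparative data, two things must happen: a by-arm report is produced, and it reaches the PIs unsealed or is discussed with them present. The text allows each of these and states neither.

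**The case against.** The strongest reply is that the plan already has the usual elements. There are closed sessions, numbered and sealed reports, and a board of three scientists or clinicians independent of the study, with signed conflict-of-interest statements. The recommendation is a vote, and members approve the report. Section 3.h.3, as the specific provision on sessions, can be read as governing the general sentence in 3.h.2. Efficacy data are mentioned only as a possibility, so there may never have been a by-arm report to protect. Nor can rewording section 3.h protect a trial whose results are already in the SAP.

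Much of this stands. It limits the point to what the procedure allows, and it means that the useful step for this trial is disclosure. It does not remove the gap. None of these safeguards says that a by-arm report bypasses the PIs, the envelope sentence leaves the decisive detail open, and the attendance statements still need reconciling.

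One limit applies: section 3.h refers to Appendix 8 for more on the DSMB, and that appendix was not in the text available to this review. A safeguard there can be neither assumed nor ruled out.

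**Conclusion.** The point holds as a weakness in a stated procedure. The text permits investigator access to interim comparative data and does not show that access occurred. Its effect on the results cannot be sized from the documents. The conclusion assumes that Appendix 8 holds no overriding rule. The change is worth making because it is cheap.

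A reader might infer more, and the documents do not support it:

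- **That PIs saw results by arm.** By-arm reporting is never stated.
- **That they saw error rates by arm.** None can exist, since errors are tracked in one arm only.
- **That secure email is a way round the sealed envelopes.** Section 3.h.4 mentions email for returning reports, not for delivering them.
- **That the recommendation is not independent.** It is a DSMB vote on a draft the members approve.
- **That the narrow result for personal utility (PRU) points to a margin chosen with data in view.** The SAP gives an upper bound of 10.13 against a margin of 10 and reports that non-inferiority was not shown. Nothing links that figure to the handling of DSMB materials.

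**What to change.** In section 3.h and, in the same words, Appendix 9:

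1. **3.h.4:** the statistician who prepares any report with data by arm sends it directly to the DSMB members, without PI approval. The PIs receive the open report only: accrual, data quality, pooled data, and the experimental-arm error statistics they need for safety management.
2. **3.h.2 and 3.h.3:** state in both that PIs and their staff attend open sessions only.
3. **3.h.5:** the DSMB Chairperson drafts the recommendation; members approve it as now.
4. **Trial report:** state whether any by-arm interim data were produced, when, and who saw them. If none were, one sentence to that effect closes the matter for this trial.

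The cost is wording in one protocol section and one appendix, plus a sentence or two in the report. No data, visits or sample size are affected. One limit remains: section 3.j.1 has the statistician reviewing all collected data weekly with the trial team, so item 1 keeps by-arm reports from the PIs but does not make the preparing statistician independent. Naming an independent statistician would go further, at the cost of that person's time.
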